5.6 Handling of Dropouts and Missing Data

Missing dates or partially missing dates will be imputed conservatively for concomitant medications and adverse events (AEs) to ensure that an AE is considered treatment emergent when possible and the duration is the longest possible duration.

Other missing data will not be imputed unless otherwise stated.

6 SUBJECT DISPOSITION

Screening status and screen failure reasons will be listed for all screened subjects.

7 DISCONTINUATION AND COMPLETION

A listing will be presented to show whether the enrolled subject completed Week 26, and Week 52 and discontinuation reason if the subject permanently discontinues study participation by data cutoff.

8 PROTOCOL DEVIATIONS

The trial's Study Specific Guideline for Managing Protocol Deviations defines protocol deviations, including whether they are minor or major. A data listing of protocol deviations will be provided for ITT population. COVID-19 pandemic related deviations will be flagged in the listing.

9 DEMOGRAPHICS AND BASELINE CHARACTERISTICS

A listing will be provided for the following demographic and baseline characteristics for ITT population:

- i. age at enrollment (year)
 - age group (≥ 18 - < 65 , ≥ 65)
 - age group (≥ 18 - < 30 , ≥ 30 - ≤ 50 , > 50)
- ii. sex (Female/Male)
- iii. ethnicity
- iv. race
- v. height (cm)
- vi. weight (kg)
- vii. BMI (kg/m^2)
- viii. baseline disease characteristics including
 1. time since diagnosis of hemophilia A (year)
 2. type of FVIII treatment for hemophilia A (prophylaxis/on-demand)
 3. any history of FVIII inhibitor (Yes/No)
 4. FVIII genotyping results
 5. number of target joints
 6. body location of target joints
 7. ambulatory assist device requirement (Yes/No)
- ix. history of liver disease (Yes/No)
- x. history of hepatitis B (Yes/No)
- xi. history of hepatitis C (Yes/No)
- xii. history of HIV (Yes/No)
- xiii. baseline FVIII activity (IU/dL)
- xiv. duration of baseline data collection periods, months
- xv. baseline annualized utilization (IU/kg/year) of exogenous FVIII replacement therapy

- xvi. baseline annualized number of FVIII infusions (infusions/year)
- xvii. baseline ABR (treated bleeds/year)
- xviii. baseline ABR (all bleeds/year)

10 MEDICAL HISTORY

Medical history will be coded using the most current version of Medical Dictionary for Regulatory Activities (MedDRA) at the time of coding. A listing will be provided for medical history data in ITT population.

11 PRIOR AND CONCOMITANT MEDICATIONS/PROCEDURES

Prior and concomitant medications are defined as follows:

- prior medication—any medication taken prior to the initiation of the investigational product and within 30 days prior to screening;
- concomitant medication—any medication taken after initiation of the investigational product.

All medications will be coded using the current version of the World Health Organization Drug (WHO Drug) Dictionary.

Prior and concomitant medication use will be listed for ITT population.

12 EXTENT OF EXPOSURE TO INVESTIGATIONAL PRODUCT

A data listing of drug exposure will be provided for ITT population.

13 EFFICACY EVALUATIONS

14 SAFETY EVALUATIONS

Safety will be assessed by adverse event reporting; clinical laboratory assessments, with particular attention to liver function; vital signs assessments; physical examinations; and immunogenicity.

14.1 Adverse Events

[REDACTED] A TEAE is defined as any AE that newly appeared or worsened in severity following initiation of investigational product administration. Adverse events will be coded in accordance with Medical Dictionary for Regulatory Activities (MedDRA).

An adverse drug reaction (ADR) is any AE for which there is a reasonable possibility that the investigational product caused the AE. The investigator will assess the causality for individual AEs, applying the guidance specified in protocol, and those assessed as study drug-related will be considered ADRs.

A serious adverse event (SAE) is any untoward medical occurrence that at any dose meets one or more of the seriousness criteria enumerated in the protocol. AE severity, not equivalent to seriousness, will be assessed using the protocol defined categories using the NCI CTCAE v4.03.

All bleeding events and suspected bleeding events, regardless of the need for exogenous FVIII therapy as treatment, should be captured in subject diaries and recorded on the designated bleeding eCRF. Bleeding events and suspected bleeding events should not be reported as adverse events, with the following exception:

- All bleeding events and suspected bleeding events which meet one or more of the criteria for being serious (refer to the protocol Section 10.2) should be reported as serious adverse events (whether or not they are bleeding events that are normal sequelae of hemophilia, and whether or not they required exogenous FVIII as treatment).

The study AE reporting period is as follows: After informed consent but prior to initiation of study treatment, only SAEs associated with any protocol-imposed interventions will be reported. After informed consent is obtained and following the administration of investigational product, the reporting period for all non-serious AEs and SAEs begins and continues for approximately 5 years or until study discontinuation/termination.

If the onset date or end date of an AE is partial, the same imputation rules described in Section 5.0 will be applied.

14.1.1 All Adverse Events

A listing of all AEs will be provided.

14.1.2 Drug-Related Adverse Events

All TEAEs assessed by investigator as investigational product related (i.e., ADRs) will be included in a listing.

14.1.3 Deaths and Serious Adverse Events

A list of subjects who died and all SAEs and SAEs assessed by investigator as investigational product related (i.e., serious ADRs) will be provided.

14.1.4 Adverse Events Causing Early Discontinuation

A list of subjects with the AEs resulting in discontinuation of study will be provided.

14.1.5 Events of Special Interest (EOSIs)

The following events of special interest, which include EOSI defined in the protocol, will be provided in a data listing for each type of EOSI.

- Transaminitis
 - ALT elevations (AE Preferred term: “Alanine aminotransferase increased”).
 - AEs of liver dysfunction, defined using the MedDRA search strategy high level term (HLT = “Liver function analyses”).
 - Potential Hy’s law cases
 - ALT or AST \geq 3x ULN and serum TBL > 2x ULN
 - Assessments of ALT/AST and TBL must be on the same day

A listing will be provided.

- Infusion related reaction, Hypersensitivity, Anaphylactic or Anaphylactoid reactions
 - Infusion related reactions, defined as AEs occurring during BMN 270 infusion or up to 48 hours post-infusion^a, will be summarized as follows:

- Subjects who receive infusion with initial rate of approximately 4 mL/min
- The rest of the subjects, i.e. subjects who receive infusion with initial rate of 1 mL/min
- All treated subjects
- Systemic hypersensitivity (Hypersensitivity [SMQ] - narrow scope), occurring during BMN 270 infusion or up to 48 hours post-infusion^a.
- Anaphylactic, or anaphylactoid reactions (Anaphylactic reaction [SMQ] – algorithmic), occurring during BMN 270 infusion or up to 48 hours post-infusion^a – listing only.
- Thromboembolic events:
 - Embolic and thrombotic events (SMQ).
 - AEs suggestive of thromboembolic events: for subjects who have FVIII elevation > 150% any time during study, a listing of clinical terms suggestive of thromboembolic events observed from the time point prior to when FVIII was elevated until FVIII falls below 150%. (The AE preferred terms are listed in Appendix 19.2.)
- Development of anti-FVIII neutralizing antibodies as measured by the Nijmegen modified Bethesda assay (Preferred term: "Anti factor VIII antibody positive", reported as EOSI)

^a If the number of hours post-infusion cannot be determined, AEs that start two days after the infusion day are excluded.

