Following completion of the infusion, vital signs will be monitored hourly ( $\pm 5$  minutes). If the vital signs are stable the catheter will be removed 8 hours after the infusion. Hemostasis at the puncture site will be established by applying pressure according to standard protocol for infusing FVIII concentrates. Subjects will remain in the clinic for at least 8 hours to observe for any immediate toxicity of the procedure; in-patient observation can be extended beyond 8 hours if needed per Investigator discretion, or the subject may transfer to a separate facility based on the evaluation and judgment of the Principal Investigator after consultation with the Medical Monitor.

Prior to discharging subjects from the clinic, the Investigator or designee should instruct subjects how to recognize signs and symptoms of potential (delayed) hypersensitivity reactions and anaphylaxis, and to contact a medical practitioner or seek emergency care in case of such an event.

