### **10.2.1 Events of Special Interest (EOSI)**

The following EOSI need to be reported to the Sponsor within 24 hours of site awareness, irrespective of seriousness, severity or causality:

- Elevation of ALT  $\geq 1.5x$  ULN or ALT  $>$  ULN &  $>2x$  baseline value, regardless of whether that elevation triggers an initiation or modification of oral corticosteroid treatment
- Thromboembolic event
- Systemic hypersensitivity, anaphylactic, or anaphylactoid reactions (refer to Appendix 1)
- Development of anti-FVIII inhibitory antibodies (inhibitors)

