## **10.3 Methods and Timing for Capturing and Assessing Safety Parameters**

### **10.3.1 Adverse Event Reporting Period**

The study AE reporting period is as follows:

- After informed consent but prior to initiation of study drug, only SAEs associated with any protocol-imposed interventions will be collected; AEs occurring during this time period should be recorded on the Medical History eCRF.
- After informed consent is obtained and following infusion of study drug, the reporting period for all non-serious AEs and SAEs begins and continues for approximately 5 years or until study discontinuation/termination, whichever is longer.

The criteria for determining, and the reporting of SAEs is provided in Section 10.2.

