### **10.5 Reporting Requirements**

#### **10.5.1 Expedited Reporting Requirements**

All SAEs and EOSI that occur during the course of the AE Reporting Period (refer to Section 10.3.1), whether or not considered related to study drug, must be reported by entering the information in the AE eCRF and submitting to BPV within 24 hours of the site becoming aware of the event. Investigators should not wait to collect information that fully documents the event before notifying BPV of an SAE. BioMarin may be required to report certain SAEs to regulatory authorities within 7 calendar days of being notified about the event; therefore, it is important that Investigators submit any information requested by BioMarin as soon as it becomes available. IND safety reports will be submitted within 7 calendar days for fatal or life-threatening unexpected suspected adverse reactions (SUSARs) and within 15 calendar days for other non-life-threatening SUSARs

---

The Sponsor is responsible for identifying, preparing and reporting all SUSARs to the relevant competent authorities, ethics committees and Investigators in accordance with the requirements identified in the Clinical Trials Regulations.

If the EDC is unavailable, all SAEs should be reported to BPV by completing the SAE Report Form and faxing or emailing the completed form to BPV within 24 hours of the site becoming aware of the event. Once the EDC is available, the information should be entered in the AE eCRF.

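### SAP 14.1.5 limits the hypersensitivity and anaphylaxis EOSI listings to 48 hours after infusion, although the protocol EOSI they claim to include has no onset window

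*SAP*

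**What the plan says.** **Protocol.** Section 10.2.1 names as an EOSI: "Systemic hypersensitivity, anaphylactic, or anaphylactoid reactions (refer to Appendix 1". Its conditions are broad: "The following EOSI need to be reported to the Sponsor within 24 hours of site awareness, irrespective of seriousness, severity or causality". The only clock in that section runs from site awareness, not from infusion. Section 10.5.1 requires prompt reporting of "All SAEs and EOSI that occur during the course of the AE Reporting Period", and section 10.3.1 says that this period "continues for approximately 5 years or until study discontinuation/termination, whichever is longer". Section 9.4.4 has the site, before discharge, "instruct subjects how to recognize signs and symptoms of potential (delayed) hypersensitivity reactions and anaphylaxis".

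**SAP.** Section 14.1.5 opens with: "The following events of special interest, which include EOSI defined in the protocol, will be provided in a data listing". Under the group for infusion-related reactions, hypersensitivity and anaphylaxis it then gives three items, all with the same time limit:
- infusion-related reactions;
- systemic hypersensitivity: "Systemic hypersensitivity (Hypersensitivity [SMQ] - narrow scope), occurring during BMN 270 infusion or up to 48 hours post-infusion";
- anaphylactic or anaphylactoid reactions, found by the algorithmic search.

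A footnote to all three excludes adverse events that start two days after the infusion day when the hours since infusion cannot be determined. Sections 14.1.1 to 14.1.3 separately provide listings of all adverse events, drug-related events, and deaths and serious events. No onset window is stated for any of these.

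**The concern.** The lead-in to SAP 14.1.5 promises the protocol's EOSI, and the items beneath it deliver a narrower set. A site can correctly report a late systemic hypersensitivity reaction as an EOSI, and the SAP's filter will then drop it from the listing for that class. Someone who finds that listing empty could reasonably conclude that no such EOSI was reported.

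The SAP gives no reason for the narrowing. A 48-hour limit is natural for infusion-related reactions, which are defined by their timing. The same phrase and footnote are attached to the next two items without comment. No other EOSI class in the section has a cut-off counted from infusion. The item on terms suggestive of thromboembolism does have a window, but it follows FVIII elevation. The anti-FVIII antibody item refers to events reported as EOSI, so the SAP already uses the site's own classification elsewhere in the section.

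**Working it through.** The documents give no figure to reproduce. The check compares the two definitions and then follows single events through them.

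**Definitions side by side**

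| | Protocol 10.2.1, 10.3.1, 10.5.1 | SAP 14.1.5 |
|---|---|---|
| Systemic hypersensitivity | No onset window; reportable for about 5 years | Narrow-scope search, infusion to 48 hours |
| Anaphylactic/anaphylactoid | No onset window; refers to Appendix 1 | Algorithmic search, infusion to 48 hours |
| Hours unknown | No rule | Onset two days after the infusion day excluded |

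**Which days the window covers.** SAP 5.3 makes the infusion date Day 1 and sets later study days as visit date − Day 1 date + 1. Two days after infusion is therefore 2 + 1 = Day 3. Let t be the clock hour on Day 1 at which the infusion ends, with t between 0 and 24 (assuming it ends on the infusion day).
- Counted from the start of Day 1, the window closes at t + 48 hours.
- Day 3 runs from hour 48 to hour 72, so its first t hours lie inside the window. With an assumed finish at noon, t = 12 and half of Day 3 is inside.
- Day 4 starts at hour 72, which is 72 − t ≥ 48 hours after the end of infusion. Onset on Day 4 or later is outside the window, apart from the limiting case of equality.

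**Following an event through the rules.** Take a systemic hypersensitivity reaction that the site reported as this EOSI and that is coded to a term in the narrow search.

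| Onset | Protocol EOSI | SAP EOSI listing | All-AE listing |
|---|---|---|---|
| Within 48 hours, time known | Yes | Yes | Yes |
| Day 3, hours unknown | Yes | No | Yes |
| Day 4 or later | Yes | No | Yes |

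The second row is excluded even though the event may have begun within 48 hours. That runs against SAP 5.6, which imputes incomplete dates so that an adverse event counts as treatment-emergent when possible.

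**Anaphylaxis separately.** In Protocol Appendix 1, criteria 2 and 3 require onset within minutes to several hours of exposure to an allergen. Criterion 1 describes an illness of acute onset but does not tie it to exposure. BMN 270 is given once, so few vector-related cases meeting criteria 2 or 3 could begin after 48 hours. Appendix 1 sets no such limit for systemic hypersensitivity, so the gap matters mainly there.

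**The case against.** **The event is still shown.** This stands. A late reaction appears in the all-AE listing, in the drug-related listing if judged related, and in the serious-event listing if serious. Site reporting to the sponsor within 24 hours of awareness does not depend on the SAP. A reader might infer that late reactions vanish from safety reporting, but they are omitted from one class listing only.

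**There is one subject.** This also stands. SAP 5.2 provides listings only, so no incidence is estimated and none can be biased. The SAP describes the analysis as ancillary to a filing based on Study 270-301. A reader might infer that the filing would understate hypersensitivity risk; nothing in the documents shows that it relies on this listing.

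**The protocol does not say reactions are expected after 48 hours.** Correct. The reference to delayed reactions in section 9.4.4 is part of discharge instructions after at least 8 hours of observation. It may mean only reactions after leaving the clinic, and 48 − 8 = 40 hours of that time lie inside the window. The mismatch rests on the missing window in section 10.2.1, not on that word.

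**An onset window is a defensible definition for a single infusion.** Partly accepted. An open-ended search would also pick up reactions to other exposures, including exogenous FVIII, which continues for 4 weeks and on demand after that. But the SAP does not present its definition as narrower than the protocol's; it says that the protocol EOSI are included. A timing flag keeps the distinction without dropping events.

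**Two further inferences to avoid.** It is tempting to say that all but 2 of roughly 260 × 7 = 1,820 days are excluded. That is a share of calendar time, not of risk, which for a single-dose product is not spread evenly over 5 years. It is also tempting to say that the all-AE listing would not mark the event as an EOSI. The SAP does not describe that listing's columns and the opening of section 14.1 is redacted, so this is unknown.

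**Conclusion.** The inconsistency is real and lies in the current text. Followed as written, SAP 14.1.5 leaves out of its class listing any protocol-defined hypersensitivity or anaphylaxis EOSI that begins more than 48 hours after infusion, and any with Day 3 onset and unknown hours. It is clearest for systemic hypersensitivity and weak for anaphylaxis.

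The practical size is small: one subject, listings only, no biased estimate, and every such event visible in at least one other listing. What remains is a class listing that can look empty when a protocol EOSI was reported. That is worth correcting because the output supports a filing and the SAP allows further interim analyses. The conclusion assumes that the 48-hour phrase is applied as a filter, as its wording indicates, and that no redacted text restores later events; the unredacted SAP contains nothing that does.

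**What to change.** In SAP 14.1.5, remove the 48-hour limit and its footnote from the systemic hypersensitivity and anaphylactic/anaphylactoid items. List all events meeting those searches, together with any that the site reported as this EOSI, regardless of onset. Add a column flagging onset within 48 hours of infusion, and keep events of uncertain timing, marked as such. Use the 48-hour window as a filter only for infusion-related reactions.

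If the sponsor prefers the narrower definition, the minimum is to state and justify it and to amend the lead-in, which would no longer be accurate for this class.

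The cost is a few words of SAP text, one program filter and one listing column. The downside is that some events unrelated to the infusion, such as reactions to exogenous FVIII, will also be listed. The flag separates late-onset events from early ones.

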5.2 Treatment Group Presentation

Only listings will be provided since only one subject was enrolled.

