5.3 Study Day Derivation

Study day is assigned as follows:

- The investigational product infusion date is designated as Day 1.
- For visit days after infusion, study day = visit date – Day 1 date + 1.
- For visit days prior to infusion, study day = visit date – Day 1 date (Thus, study days for screening visits are negative numbers.)

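### SAP 14.1.5 footnote a can leave a reaction that began within 48 hours out of the infusion-reaction listings when its onset hour is unknown; the effect is small and cheap to correct

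*SAP*

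**What the plan says.** SAP 14.1.5 (Events of Special Interest) sets a time window for three outputs. The first reads: "Infusion related reactions, defined as AEs occurring during BMN 270 infusion or up to 48 hours post-infusion". Systemic hypersensitivity and anaphylactic or anaphylactoid reactions carry the same window, and footnote a is attached to all three. It states: "If the number of hours post-infusion cannot be determined, AEs that start two days after the infusion day are excluded". The SAP gives no reason for the cut and no alternative listing.

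Three other places bear on it:

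- SAP 5.3 fixes the day count: "The investigational product infusion date is designated as Day 1". Two days after the infusion day is therefore Day 3.
- SAP 5.6 resolves missing or partial adverse event dates conservatively, "to ensure that an AE is considered treatment emergent when possible and the duration is the longest possible duration".
- SAP 5.2 limits the output: "Only listings will be provided since only one subject was enrolled".

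**The concern.** A 48-hour window that opens partway through Day 1 closes partway through Day 3. An event known to have started on Day 3, with no clock time, may lie on either side of the limit. The footnote treats all such events as outside.

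The listings in 14.1.5 are where a reader looks for infusion reactions, and they support a marketing application (SAP 4). With one subject, a single omitted event could turn a listing with an entry into an empty one.

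Day 3 is also a day on which a clock time may well be missing. Protocol 9.4.4 requires at least 8 hours of observation in the clinic, and the next visit in Protocol Table 9.1.2 is Day 4. A Day 3 onset would usually happen away from the site. That a time is then less likely to be recorded is an inference; the documents do not say whether the adverse event form captures onset time.

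**Working it through.** The plan states no figure to reproduce. The check is clock arithmetic.

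Inputs:

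- Window: 48 hours after infusion (SAP 14.1.5).
- Infusion day is Day 1 (SAP 5.3); untimed Day 3 events are excluded (SAP 14.1.5, footnote a).
- t, the clock hour on Day 1 at which the infusion ends. The documents do not give it, so 09:00, 12:00 and 17:00 are assumed.

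Formulas:

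- The window closes at hour t on Day 3, so the share of Day 3 inside it is t/24.
- Untimed events are kept only to the end of Day 2, so the effective window is 48 − t hours.
- The share of the 48 hours lost is t/48.
- If untimed Day 3 events were kept instead, the cut-off would fall at 72 − t hours, an overreach of 24 − t hours.

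| Infusion end (assumed) | Share of Day 3 inside 48 h | Effective window under the footnote | Share of 48 h lost | Cut-off if Day 3 is kept | Overreach |
|---|---|---|---|---|---|
| 09:00 | 9/24 = 37.5% | 48 − 9 = 39 h | 9/48 = 18.8% | 72 − 9 = 63 h | 15 h |
| 12:00 | 12/24 = 50% | 48 − 12 = 36 h | 12/48 = 25% | 72 − 12 = 60 h | 12 h |
| 17:00 | 17/24 = 70.8% | 48 − 17 = 31 h | 17/48 = 35.4% | 72 − 17 = 55 h | 7 h |

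Over all values of t from 0 to 24, the effective window lies between 24 and 48 hours. It reaches 48 only if the infusion ends at midnight at the start of Day 1.

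Direction of the error: the end of Day 2 falls 48 − t hours after infusion, which never exceeds 48. Everything that starts after infusion on Day 1, or at any time on Day 2, is therefore inside the window. No wrongly kept post-infusion event offsets the Day 3 events that are wrongly dropped.

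**The case against.** The strongest reply is that, with the hour unknown, any rule is a convention, and the SAP states its own in advance. At an assumed end of 09:00, 62.5% of Day 3 (15/24) is outside the window, so if onset were uniform over the day, exclusion would be right more often than wrong. Keeping every untimed Day 3 event swaps one misclassification for another, reaching 7 to 15 hours past the limit in the assumed cases. For anaphylaxis a first onset on Day 3 is a weak example, since Protocol Appendix 1 ties two of its three criteria to onset within hours of exposure. These points are fair. They do not rescue the footnote: exclusion hides a possible within-window reaction from the listing built to show it, while inclusion with a flag leaves the uncertainty in view.

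The reply also rules out several stronger readings that a reader might infer:

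- *Reactions are undercounted.* The plan produces no count or rate. Although 14.1.5 speaks of summarizing infusion reactions, its lead-in promises data listings, SAP 5.2 allows only listings, and the synopsis rules out efficacy summary tables because one subject was enrolled. A reaction is lost only if an untimed event in fact began on Day 3 before hour t.
- *Events vanish from the safety output.* SAP 14.1.1 says: "A listing of all AEs will be provided". Related and serious events are also listed, under 14.1.2 and 14.1.3.
- *Safety reporting suffers.* The hypersensitivity event of special interest in Protocol 10.2.1 has no 48-hour limit, so 24-hour reporting to the sponsor does not depend on the footnote.
- *The footnote contradicts SAP 5.6.* That section covers missing dates, for treatment emergence and duration. A Day 3 event with a full date but no hour has no missing date and is treatment emergent under either rule.
- *Between 37.5% and 70.8% of reactions are lost.* Those are shares of clock hours on one day. The documents give neither the distribution of onset times nor the frequency of missing hours.

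**Conclusion.** The point holds as a minor flaw. For untimed events the footnote shortens a 48-hour window to 48 − t hours (31 to 39 hours for assumed ends of 17:00 to 09:00), and its post-infusion error runs only toward omission. It can leave a qualifying reaction out of the infusion-reaction, hypersensitivity and anaphylaxis listings. That is out of keeping with the inclusive spirit of SAP 5.6 without contradicting it.

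The consequence is at most a missing row or so in special-interest listings for one treated subject, with the event still visible in the listing of all adverse events. The size figures rest on the assumed end times and on the infusion ending on Day 1. The direction of the error does not depend on which hour is assumed.

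**What to change.** Reword footnote a so that, when the hours after infusion cannot be determined, adverse events starting on the infusion day or on either of the next two calendar days stay in these listings and carry a flag such as *onset time unknown; may fall outside 48 h*. This covers the full 48 hours for any end time. If the sponsor prefers exclusion, the footnote should at least say why.

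The cost is one footnote and one flag. The downside is that untimed events up to 72 − t hours after infusion (55 to 63 hours in the assumed cases) may be listed; the flag tells the reader which they are.
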